4.2.3 Handling of missing data

No data will be imputed for any effectiveness or safety analyses except for the analyses of the HCV RNA endpoints and certain PRO endpoints. The discussion of missing data imputation for the PRO endpoints is included in section 4.2.7.2.3.

HCV RNA values will be selected for an RVR, EOTR and SVR analysis based on visit windows as defined in Table 3. When there is no HCV RNA value in a visit window based on defined visit windows, the closest values before and after the window, regardless of the value chosen for the subsequent and preceding window, will be used for the flanking imputation described below. For analysis of RVR, EOT and SVR, if a subject has a missing HCV RNA value at a post-Day 1 visit but with undetectable or unquantifiable (\leq 50 IU/mL) HCV RNA levels at both the preceding value and succeeding value, the HCV RNA level will be considered undetectable or unquantifiable, respectively, at this visit for this subject. In addition, if a subject has an unquantifiable HCV RNA level at the preceding value and an undetectable HCV RNA level at the succeeding value, or vice versa, the HCV RNA level will be imputed as unquantifiable at this visit for this subject.

For analyses of RVR, subjects still missing a value for the visit after flanking imputation will be imputed as a failure. For EoTR and SVR analysis, if there is no value in the appropriate window after flanking imputation but there is an HCV RNA value after the window, then it will be imputed into the EoTR or SVR window respectively. Subsequent to this flanking imputation, if a subject is missing a value for the visit window associated with the analysis, the subject will be imputed as a visit failure (i.e., not undetectable or unquantifiable).

If a subject starts another treatment for HCV, then all HCV RNA values for this subject measured on or after the start date of the new HCV treatment will be excluded from analyses. The subject will be considered a failure for summaries of viral response at all time points after the start of the new HCV treatment.

Due to the non-interventional nature of this study several different methods for determination of the HCV RNA value can be applied. For the purpose of the statistical analysis, a HCV RNA measurement is considered ≤ 50 IU/mL,

- if a PCR test was used

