4.2.5 Patient Disposition

The frequencies of patients belonging to the different populations (i.e. EP, TP, CP, CPSFU; SP) will be summarized by genotype and cirrhosis status and overall using the EP analysis groups as specified in section 4.2.1. The reasons for exclusion from a particular population will be also summarized in the frequency tables. Additionally, information on patient disposition will be listed.

Furthermore the frequency of patients not completing the study as defined per protocol (i.e. no HCV RNA assessment performed at least 10 weeks post-treatment), will be summarized by treatment regimen and cirrhosis status and additionally by genotype and cirrhosis status and overall for the SP and CP. The reasons for not completing the study as entered on the CRF will be displayed (i.e. failure to return, insufficient virological response (HCV RNA detectable at End of treatment, Relapse post-treatment), patient never started treatment, withdrawn consent, death, other).

Additionally, the main reason for early termination of the ABBVIE regimen (AE or SAE [Physician decision], virological non-response [Physician decision], rebound or breakthrough [Physician decision], resistance to DAA [Physician decision], patient refused to continue treatment, patient withdrew consent to participate in the study, lost to follow-up, other, unknown [if actual duration is shortened for more than 7 days]) and Ribavirin (Anemia, Nausea/Vomiting, Rash, Other) will be summarized by treatment regimen and cirrhosis status and additionally by genotype and cirrhosis status and overall for the following different analysis populations: CP and SP.

Finally the study regimens assigned at baseline will be summarized (a) by genotype and cirrhosis status and (b) by genotype and pre-treatment status (treatment naïve vs treatment experienced) for CP and SP.

An overview of Tables is given in Table 6.

Table 6 Overview of Outputs for Patient Disposition

Output Title	Output Short Name	Analysis Population
Patient Disposition by Genotype and Cirrhosis Status – EP - <country>	tdis_<c>_gc_ep	Patients Enrolled
Listing of Patient Disposition - EP- <country>	ldis_<c>_ep	Patients Enrolled
Premature Termination of the Study and its Main Reason by <Treatment Regimen/ Genotype> and Cirrhosis Status - CP - <country>	tps_<c>_<t/g>c_cp	Core population

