- Other co-morbidities (every patient not reporting the respective co-morbidity is considered as not having the respective co-morbidity)
 - Depression (No [reference], Yes)

- Diabetes mellitus (No [reference], Type 1/Type 2)
 - Hypertension (No [reference], Yes)
 - Immunologically mediated disease (No [reference], Yes)
 - Hypothyroidism (No [reference], Yes)
 - Alcohol use (None [reference], Yes –occasional, Yes –regular, Exdrinker)
 - Key clinical chemistry and hematology laboratory variables at baseline
 - ALT ratio (continuous, see 4.2.6.5)
 - AST ratio (continuous, see 4.2.6.5)
 - Platelets [$10^9/L$] (continuous)
 - Prior treatment status (HCV treatment naïve [reference], HCV treatment experienced)

Additionally, an interaction term for cirrhosis status and genotype will be considered. If the most recent stage of liver fibrosis status (No cirrhosis/Transition to cirrhosis vs Cirrhosis), the genotype (G4, G1b vs G1a) or the interaction of both remains in the final model, then additional MLR might be considered for the subgroups concerned, taking into account the treatment regimen (e.g. in cirrhotic G1 patients: RBV vs no RBV and 12 wks vs 24 weeks).

The categories pre-specified above could be modified in the analyses if this is supported by the data (e.g. categories could be combined, if their impact on SVR12 is similar). Furthermore, continuous variables can be replaced by categorical variables.

Adherence

Adherence will be displayed for the CP by genotype and cirrhosis status and for the SP by treatment regimen and cirrhosis status. Summary statistics (n, mean, median, standard deviation [SD], and range) will be generated for continuous variable. Numbers and percentages of patients will be presented for categorical variables.

- Adherence to Abbvie regimen (% of target dose [adherence=cumulated number of pills taken /(initial prescribed number of pills x planned duration)])
 - >105%
 - >95%--<=105%
 - >80%--<=95%
 - >50%--<=80%
 - <=50%
- Adherence to ribavirin (% of target dose [adherence=cumulated dose taken /(initial prescribed dose x planned duration)])

- >105%
 - >95%-<=105%
 - >80%-<=95%
 - >50%-<=80%
 - <=50%
- Percentage of actual treatment duration in relation to the target duration of ABBVIE regimen taken
- Deviating duration of ABBVIE regimen
 - Early discontinuation (actual duration is shortened for more than 7 days)
 - Not deviated
 - Exceedance (actual duration is prolonged for more than 7 days)

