- Method used to document adherence (Interview, Diary)
- Percentage of actual days with treatment with RBV in relation to the planned duration
- Ribavirin earlier discontinued than ABBVIE regimen
- Initial dose of Ribavirin
 - 1000 mg/day
 - 1200 mg/day
 - XXX
- Cumulative dose of Ribavirin (g)
- Dose modifications/termination of RBV [in patients taking RBV, for a patient more than one dose modification and its main reason could be reported, but for each single reason the patient is counted only once] (Total number of patients with lower dose than highest previous dose [including patients who stopped the treatment earlier], Anemia, Nausea/Vomiting, Rash, Other [including patients who discontinued ABBVIE regimen earlier, but did not stop the RBV treatment before the ABBVIE regimen])

In addition to the summary statistics of the adherence variables, logistic regression analyses will be performed for the following adherence variables: "adherence to Abbvie regimen" in all patients of the CP, "adherence to ribavirin" in all patients of the CP taking RBV, each categorized as follows: >=95%, >80%-<=95%, <=80% to investigate the additional impact of overall treatment adherence on SVR12. The categories may be changed if they are sparsely filled. Adherence will be included as mandatory covariate in addition to the baseline explanatory variables already mentioned above. Also the same methods will be applied as described above.

An overview of Tables is given in Table 8.

Table 8 Overview of Outputs for Primary and Secondary Effectiveness Analysis

Output Title	Output Short Name	Analysis Population
Virological Response Rates by Genotype and Cirrhosis Status – CP/CPSFU - <country>	tvr_<c>_gc_cp	Core population/ Core population with sufficient follow-up data
Virological Response Rates by Genotype and Cirrhosis Status in Patients who Completed ABBVIE Regimen – CP/CPSFU - <country>	tvr_<c>_gc_cp_ARC	Core population/ Core population with sufficient follow-up data: patients who completed ABBVIE regimen
Virological Response Rates – NCP - <country>	tvr_<c>_ncp	Non-core population
Relapse Rates by Genotype and Cirrhosis Status – CP - <country>	trr_<c>_gc_cp	Core population
Non-Response Rates by Genotype and Cirrhosis Status – CP - <country>	tnrr_<c>_gc_cp	Core population
Non-Response Rates by Genotype and Cirrhosis Status in Patients who Completed ABBVIE Regimen – CP - <country>	tnrr_<c>_gc_cp_ARC	Core population: patients who completed ABBVIE regimen

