Impact of Patient and Disease Characteristics on SVR12 – CP - <country>	tis_<c>_cp	Core population
Adherence by Genotype and Cirrhosis Status - CP - <country>	tah_<c>_gc_cp	Core population
Adherence by Treatment Regimen and Cirrhosis Status - SP - <country>	tah_<c>_gc_sp	Safety population
Impact of Adherence to Abbvie Regimen on SVR12 – CP - <country>	tiaa_<c>_cp	Core population
Impact of Adherence to Ribavirin on SVR12 in patients taking RBV – CP - <country>	tiar_<c>_cp_RBV	Core population: patients taking RBV

The layouts of the tables mentioned above are provided in Part II of the SAP (Table Shells).

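### The adherence score in the SVR12 regression divides by planned duration, so an early enough stop for virologic failure lowers a fully compliant patient's adherence category, and neither listed adherence model removes this

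*SAP*

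**What the plan says.** Protocol 9.3.2 defines adherence as cumulative dose over target dose. SAP 4.2.7.2.1 implements this for the ABBVIE REGIMEN as "adherence=cumulated number of pills taken /(initial prescribed number of pills x planned duration", and RBV adherence has the same denominator structure. Two logistic regressions then use the scores, one in all core-population (CP) patients and one in CP patients taking RBV, "each categorized as follows: >=95%, >80%-<=95%, <=80% to investigate the additional impact of overall treatment adherence on SVR12". The score cannot be dropped from the model: "Adherence will be included as mandatory covariate in addition to the baseline explanatory variables already mentioned above". All other covariates are baseline characteristics.

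SAP 4.2.5 lists among the reasons for stopping the ABBVIE REGIMEN early "virological non-response [Physician decision], rebound or breakthrough [Physician decision], resistance to DAA [Physician decision". No CP exclusion in SAP 4.2.1 concerns early stopping, and 4.2.5 tabulates early termination within the CP, so these patients are in the models.

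Table 8 lists two adherence models: "Impact of Adherence to Abbvie Regimen on SVR12" and its RBV counterpart. Completer-only versions are listed for the response and non-response tables, not for these models.

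**The concern.** Dividing by planned duration describes exposure well. As an explanatory variable for SVR12 it combines two things: doses missed while on treatment, and treatment not given after a stop. When the stop was made because the virus had not responded or had rebounded, the failure came first and the low score followed. The coefficient then partly measures failure against itself, in a known direction.

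The influence of adherence on outcome is part of the research question (Protocol 8.1) and is secondary objective 4 (SAP 2). These regressions are its planned test, and Protocol 7.2 expects the adherence data to help physicians manage patients. A reader would naturally take the coefficient to be about pill-taking.

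**Working it through.** **Figures in the plan.** The documents give none for the adherence models. The only figure borrowed here is the 417 evaluable patients of SAP 3.2. It reproduces: at 90% SVR12 the Clopper-Pearson limits are 86.71 and 92.71, width 6.00, and 417/0.95 rounds up to 439 against the stated 440. The point does not depend on it.

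**Score of a patient who takes every pill until stop day s.** Score = s / planned days, with 84 days for 12 weeks and 168 for 24 weeks.

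| Category | 12-week course | 24-week course |
|---|---|---|
| 80% or less | to day 67 (67/84 = 79.8%) | to day 134 (134/168 = 79.8%) |
| middle | days 68–79 (81.0% to 94.0%) | days 135–159 (80.4% to 94.6%) |
| top | from day 80 (95.2%) | from day 160 (95.2%) |

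Stops at weeks 4, 6 and 8 of 12 score 33%, 50% and 67%. With pills due up to the last actual dose as denominator, the same patient scores 100% on every stop day.

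**Illustrative size.** Let k be the virologic stops scored 80% or less, L the other patients scored there, and p their failure risk. The odds of failure in that category are L·p / (L·(1−p)) without the k patients and (k + L·p) / (L·(1−p)) with them. The odds ratio against the top category is therefore multiplied by 1 + k/(L·p), whatever the background failure rate.

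All inputs are assumptions: L = 21 to 42 (5% to 10% of 417) and p mostly 40%. L includes stops for adverse events, refusal and loss to follow-up. For a missing SVR12 value SAP 4.2.3 says, after its imputation steps, "if a subject is missing a value for the visit window associated with the analysis, the subject will be imputed as a visit failure", so p is probably well above background.

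- k = 0: 1.00.
- p = 40%: k = 1 gives 1.06–1.12; k = 2 gives 1.12–1.24; k = 4 gives 1 + 4/16.8 = 1.24 to 1 + 4/8.4 = 1.48.
- k = 4 at p = 20%: 1.48–1.95. At p = 60%: 1.16–1.32.
- Upper-end case, p equal to a background of 5% to 10%, k = 4: 1.95–4.81.

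**Worked case** (unadjusted; middle group 42, background failure 10%, p = 40%, k = 4, L = 21). The top group has 417 − 42 − 21 − 4 = 350 patients, 35 of them failures.

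- Without the four patients: (8.4/12.6)/(35/315) = 6.00.
- With SAP scoring: (12.4/12.6)/(35/315) = 8.86, or 7.43 at L = 42.
- With only those four rescored to the top category: (8.4/12.6)/(39/315) = 5.38.

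The association is strong without these patients, so in this example they inflate it rather than create it.

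**What these figures do not show.** The factor compares including the k patients with deleting them. The 5.38 rescores only them, whereas an on-treatment measure rescores every early stop. Neither figure measures the effect of the model proposed below.

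**The case against.** The regression uses the protocol's own measure, and its stated aim is overall treatment adherence, in which persistence is a legitimate component. It is exploratory. The affected group may be tiny: Protocol 7.1 reports a low discontinuation rate, and Protocol 9.1 with Annexes 3 and 4 gives a 12-week course one interim on-treatment window before end of treatment. In the p = 40%, k = 4 examples with 10% background, the shift in the log odds ratio (0.39 at L = 21, 0.21 at L = 42) is below one standard error (0.44 and 0.35). Those examples also imply overall SVR12 of about 88% and 86% (51.6 and 57.9 failures of 417), below the planning value of at least 90%. Stop reasons are already tabulated (SAP 4.2.5 and 4.2.8.1).

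Most of this stands, and it limits the size and the severity. It does not change the direction of the bias. Nor does it let a reader separate missed pills from treatment withdrawn after failure, because the planned tables do not cross stop reason with adherence category.

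Three stronger readings are tempting, and the documents do not support them:

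- That every compliant patient stopped for virologic failure is scored 80% or less. Later stops fall in the middle or top category.
- That the SAP departs from the protocol. It follows the protocol's definition.
- That any adherence effect found would be an artefact of a known size. The number of such stops is not given, and the odds ratios above rest on assumed inputs.

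**Conclusion.** The point holds in bounded form. For compliant patients stopped for virologic failure by day 67 of 84 (134 of 168), or on days 68 to 79 (135 to 159) with a smaller downgrade, the outcome sets the adherence category and pushes the coefficient towards an adherence effect. Neither model in Table 8 removes this. The statement rests on the SAP text and Table 8; the Part II table shells were not available.

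The size is unknown and may be zero. Stops for adverse events, refusal or loss to follow-up are not part of this claim. The primary SVR12 estimate is untouched. Severity is minor to should-fix: the mechanism is certain, the size is not, the analysis is exploratory, and the remedy is cheap.

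**What to change.** Keep the target-dose measure for the descriptive table and as one model. Then:

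1. Add one regression per adherence variable with on-treatment adherence, and base statements about pill-taking on it. For the ABBVIE REGIMEN: pills taken / (initial prescribed daily pills × actual days from first to last ABBVIE REGIMEN dose). For RBV: dose taken / (initial prescribed daily dose × the same actual ABBVIE REGIMEN days), so that stopping RBV before the ABBVIE REGIMEN still lowers RBV adherence.
2. Add to the planned stop-reason tables one cross-tabulation, by adherence category, of virologic-failure stops and other SVR12 failures. For RBV it must use the ABBVIE REGIMEN stop reason, because the RBV list has no virologic category: "and Ribavirin (Anemia, Nausea/Vomiting, Rash, Other) will be summarized by treatment regimen and cirrhosis status".
3. Minor edit: the model categories overlap at exactly 95%. Use >95%, >80–95% and ≤80%, in line with the descriptive bands.

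Deleting the virologic stops is not a substitute. It selects on outcome and biases towards no effect.

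The cost is analysis work only. The SAP already uses amount taken and stop reasons, and actual duration is available through "Percentage of actual treatment duration in relation to the target duration of ABBVIE regimen taken".

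The downside is real. The on-treatment measure ignores non-persistence: a patient who refuses treatment after two weeks can score 100%. It also moves other compliant early stops out of the ≤80% category, which may become sparse. In the worked case, if 50% or 75% of the 21 other low scorers move, 10.5 or 5.25 expected patients remain, and the standard error of the log odds ratio rises from about 0.44 to about 0.65 or 0.90. The new model therefore sits beside the target-dose model and does not replace it.

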#### **8.2.2 Secondary Objectives**

2. To provide real world evidence for predictive factors of virological response
3. To describe the pattern of real world use of the ABBVIE REGIMEN ± RBV with respect to different patient and treatment characteristics

---

Confidential Information

No use or disclose outside AbbVie is permitted without prior written authorization from AbbVie

4. To evaluate the influence of adherence on treatment outcome in routine clinical practice
5. To evaluate the contribution of the patient support program (PSP) to disease control, treatment continuation over time, patient satisfaction and PSP utilization
6. To assess viral resistance patterns

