### 9.3.2 Secondary Variables

- Type of treatment regimen (± Dasabuvir, ± RBV, intended and actual combination, dose and duration)
- Adherence  
*A period of 7 days in a row of missed intake of the ABBVIE Regimen during the time between documented first dose and last dose will issue a medication error report.*
  - Percentage of the DAA dose taken in relation to the target dose of DAA (cumulative dose taken divided by target dose in percent)
  - Percentage of the RBV dose taken in relation to the target dose of RBV (cumulative dose taken divided by target dose in percent)
  - Percentage of missed RBV treatment days in relation to the target number of RBV treatment days
- PAM-13, BMQ, PSP satisfaction and utilization questionnaires
- Portal hypertension in cirrhotic patients as assessed by hepatic venous pressure gradient (HVPG) and/or clinical symptoms prior to treatment initiation, at EoT, as well as 12 and 24 weeks after EoT
- Resistant virus variants at post-baseline time points compared to baseline

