#### 9.7.3.3 Statistical Methods for Analysis of Effectiveness Variables

The simple percentage of patients achieving SVR12 will be calculated and an exact two-sided 95% confidence interval (CI) of the percentage will be computed based on the Clopper-Pearson method.

Corresponding methods will be used for other response rates (EoT response rate, relapse rate, viral breakthrough). The relapse rates will be estimated in patients of the CP analysis groups with EoT response and sufficient HCV RNA measurements post-treatment. Viral breakthrough rates will be estimated in all patients of the CP analysis groups, who have at least one undetectable HCV RNA measurement on-treatment and at least one on-treatment or EoT measurement thereafter.

Univariate and multiple logistic regression (MLR) methods will be used to investigate the impact of the following explanatory covariates on SVR12:

- Key demographic information
- Mode of CHC infection
- HCV RNA level at baseline
- Most recent stage of liver fibrosis
- HCV genotype and subtype (if available)
- Type of treating institute
- Liver and/or CHC related co-morbidities
- Key clinical chemistry and hematology laboratory variables at baseline
- In treatment experienced patients only:
  - Most recent prior treatment for CHC
  - Outcome of most recent prior CHC treatment

Further details and additional covariates will be specified in the SAP.

These analyses will be of exploratory nature, data driven, and will be repeatedly performed for various CP Analysis Groups, since not each covariate might be predictive in each patient group. Furthermore, the fact that treatment regimens will differ in the various patient groups has to be taken into account, when selecting the patient groups for each MLR analysis. Backward selection procedures will be applied to generate the final MLR models which consider only covariates in the selection procedure with a p-value

---

Confidential Information

No use or disclose outside AbbVie is permitted without prior written authorization from AbbVie

<0.25 in the corresponding univariate logistic regression analysis. A p-value <0.05 will be used for the covariates to stay in the model in a backward elimination step. Logistic regression methods will also be used to investigate the impact of treatment adherence on SVR12.

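### Adherence is derived as a continuous percentage but enters the SVR12 regressions only as three bands that overlap at 95%, which costs power if its effect is graded

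*SAP*

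**What the plan says.** Adherence is part of the research question (Protocol 8.1) and is secondary objective 4: "To evaluate the influence of adherence on treatment outcome in routine clinical practice" (Protocol 8.2.2). Protocol 9.3.2 defines it on a continuous scale. Protocol 9.7.3.3 asks for logistic regression and prescribes no bands: "Logistic regression methods will also be used to investigate the impact of treatment adherence on SVR12".

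SAP 4.2.7.2.1 keeps the continuous derivation ("adherence=cumulated number of pills taken /(initial prescribed number of pills x planned duration" for the regimen, and an analogous dose ratio for ribavirin). It summarises adherence in five bands, with ≤50% shown apart from >50% to ≤80%. For the regressions there are two models: regimen adherence in the core population (CP), and ribavirin adherence in CP patients taking ribavirin. In each model adherence is "each categorized as follows: >=95%, >80%-<=95%, <=80% to investigate the additional impact of overall treatment adherence on SVR12". Two further sentences matter:

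- "Adherence will be included as mandatory covariate in addition to the baseline explanatory variables already mentioned above". The term is forced, so backward elimination does not act on it.
- "The categories may be changed if they are sparsely filled". No rule says how.

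The same section lists age, weight, BMI, years since diagnosis, ALT and AST ratios and platelets as continuous by default, with the general permission that "Furthermore, continuous variables can be replaced by categorical variables". It describes the regressions as exploratory and data driven.

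**The concern.** The covariate that objective 4 is about gets a coarser coding than the adjustment covariates beside it, and no reason is given for the cut points. If SVR12 declines gradually with missed dose, the bands discard information and use 2 degrees of freedom where 1 would do. A study sized for an SVR12 of 90% to 95% expects few failures, so a real graded effect is more likely to be missed. The output would be two imprecise odds ratios, one of them resting on a small group.

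Two smaller points need no assumption. A value of exactly 95% satisfies both of the upper two bands, whereas the descriptive table starts its corresponding band strictly above 95%. And the bands may be redrawn after the data are seen. The sentence applying the same methods as for the baseline covariates may also bring in the earlier permission to combine categories whose impact on SVR12 looks similar, which would make the choice depend on the outcome.

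**Working it through.** **1. The plan's own figure.** The only sizing is the width of the Clopper-Pearson interval (Protocol 9.5, SAP 3.2). Beta quantiles with x = n × p give:

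- n = 417, 90%: 86.71 to 92.71, width 6.00 (as stated)
- n = 238, 95%: 91.41 to 97.40, width 5.99 (as stated)
- n = 334, 95%: 92.08 to 97.08, width 4.99 before rounding the limits (5.00 stated)
- 417 / 0.95 = 438.9, so 439 (440 stated)

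These reproduce. No power is stated for the adherence regression.

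**2. Information available.** Expected failures at n = 417 are 417 × 0.10 = 41.7 and 417 × 0.05 = 20.9, so about 21 to 42.

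**3. Models compared.** Both use likelihood-ratio tests at an assumed two-sided 5%, with no other covariates.

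- Bands: logit P(SVR12) = b0 + b1·I(80–95%) + b2·I(≤80%), 2 df
- Continuous: logit P(SVR12) = b0 + b·(percentage or shortfall)/10, 1 df

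**4. Graded effect, first set of assumptions** (1,000 runs per cell; Monte Carlo error of each power at most √(0.25/1000) = 1.6 points). Assumed shares in ≥95% / 80–95% / ≤80% are 85/10/5, 75/15/10, 92/5/3 or 60/25/15. The lowest band is spread evenly over 5–80%. Overall SVR12 is 90% or 95%, n is 417 or 200, and the slope is 0.1 to 0.5 per 10 points. Results for 85/10/5 at n = 417:

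| SVR12 | Slope | Continuous | Three bands | Loss |
|---|---|---|---|---|
| 90% | 0.1 | 19.1% | 13.2% | 5.9 |
| 90% | 0.2 | 50.6% | 38.2% | 12.4 |
| 90% | 0.3 | 88.6% | 75.1% | 13.5 |
| 90% | 0.4 | 98.3% | 95.1% | 3.2 |
| 95% | 0.2 | 38.8% | 29.8% | 9.0 |
| 95% | 0.3 | 73.1% | 61.3% | 11.8 |

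Over all 80 scenarios the loss is 0 to 16.5 points (median 7.4). In the 35 where continuous power is 30% to 90%, it is 6.8 to 16.5 (median 12.4). With beta-shaped adherence it is 0 to about 22.

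**5. Graded effect, second set of assumptions.** n = 417, with 8% of patients at 80–95% and 4% at ≤80% (0.04 × 417 ≈ 17 patients). SVR12 of 90% or 95% is set at full adherence.

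- Odds ratio 1.3 per 10% missed: 54% (bands) v 70% (continuous) at 90%; 40% v 54% at 95%. Repeat runs gave 55% v 71% and 56% v 70% at 90%, and 42% v 55% and 42% v 54% at 95%.
- Odds ratio 1.4: 78% v 89% at 90%; 66% v 78% at 95%.

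**6. Source of the loss** (85/10/5, n = 417, 90%, slope 0.3). Giving ≤50% its own band (3 df) yields 76.1% against 75.1%, so pooling within the lowest band is not the main cause. A 1-df trend over the three bands yields 78.5%. Of the 13.5 points, 78.5 − 75.1 = 3.4 come back by saving a degree of freedom. The other 88.6 − 78.5 = 10.1 come back only with the continuous value.

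**7. Test size.** With no effect, n = 200 and SVR12 95%, the bands reject in 2.2% and the continuous term in 5.6% of runs (a repeat gave 2.1% v 6.5%). At n = 417, 95%, with 2% and 5% in the lower bands, the figures are 2.8% v 5.4%. At n = 417 and 90% the sizes are similar, so there the gain is like for like.

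**8. Step effects.** With a flat step at 80% the two are equal (53% v 53%; 76% v 75%). With a flat step at 95% the bands win: 52% v 33%, and 69% v 45% at an odds ratio of 3. In the first set, steps at the SAP's cut points gave losses of about −7 to +2.

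**9. What low adherence means.** The denominator is planned duration. A patient on a 12-week plan with perfect intake who stops at week 6 scores 6/12 = 50%. SAP 4.2.5 lists virological non-response and rebound or breakthrough among the reasons for stopping, and SAP 4.2.3 counts a still-missing SVR12 as failure. Very low adherence can therefore be a consequence of failure.

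**The case against.** The strongest reply is that nothing stated is missed. The regressions are exploratory, neither document sets a power, alpha or effect size for objective 4, and banded adherence complies with the protocol's call for logistic regression. That stands: this is an efficiency weakness, not an error.

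Several other objections also stand, wholly or in part:

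- The size of the loss cannot be derived from the documents, and the simulations omit the planned baseline covariates, which would lower power for both codings. The absolute figures do not transfer to the planned models.
- Adherence comes from interview or diary, so the percentage is imprecise. Protocol 9.4.1.2 records ribavirin adherence as yes/no although 9.3.2 defines a percentage. Both codings need that percentage, so neither gains from this.
- A linear shortfall gives most leverage to the few patients with very low intake, and some of the extra power may detect reverse causation. The fix has to address this.

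A reader might infer that pooling 10% with 78% intake causes the loss; step 6 shows otherwise under a linear effect. A reader might also infer that the SAP will merge bands and lose the low end. It says only that bands may change if sparse, and the five-band table and the range keep the low end visible.

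**Conclusion.** The point holds as a cheap improvement to an exploratory analysis. A continuous percentage is reduced to three bands that overlap at exactly 95% and can be redrawn without a rule. If the effect on the log-odds is graded, this costs roughly 7 to 16 points of power in mid-power settings and 0 to about 22 across the linear settings tried. Most of that comes from discarding the continuous value, with a smaller part from the extra degree of freedom. The figures rest on assumed adherence distributions, slopes, a 5% test and no other covariates.

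Stronger readings are not supported. A reader might take the loss as a fixed property of the plan, but it vanishes for a flat step at 80% and reverses for a flat step at 95%. A reader might also take the gain in a small ribavirin subset at face value. At n = 200 (itself an assumed size) and 95% SVR12, part of it reflects unequal test size.

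**What to change.** In the adherence paragraph of SAP 4.2.7.2.1:

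1. Make the mandatory adherence covariate the continuous dose shortfall, max(0, 100 − % of target dose), per 10 points. Test it with 1 df in both models (regimen in the CP; ribavirin in CP patients taking ribavirin) and report the odds ratio per 10 points missed. Intake above 100% then counts as full adherence.
2. Pre-specify a shape check, such as a restricted spline or a comparison with the bands.
3. Add a sensitivity analysis excluding patients who stopped early for virological failure, and caution that low adherence against planned duration can follow from failure.
4. Keep the three bands as a supportive display with non-overlapping limits: >95%, >80% to ≤95%, ≤80%.
5. State that any re-banding after the data are seen is for display and does not drive the inference.

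The cost is SAP wording and some additional model lines in tables tiaa and tiar, with no new data. The downside is less power if the true effect is a flat step at 95%, and leverage from the few patients with very low intake. The retained bands and the shape check would show the first, and the sensitivity analysis addresses part of the second.
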